4.8 Outcome Measures

4.8.1 Primary Outcome

The primary outcome is SSI, guided by the CDC's National Healthcare Safety Network reporting criteria (2017),²⁵ which includes superficial incisional SSI within 30 days and deep incisional or organ/space SSI within 90 days of fracture surgery (Table 3). Since the management of some fractures may have more than one operative procedure as part of an intentionally staged surgical plan (e.g., multiple irrigation and debridements, wound closures, temporary stabilization surgeries, definitive fixation surgery), the primary outcome will include any SSI event from the date of fracture to the end of the 30- and 90-day post-operative surveillance periods from their definitive fracture management surgery. For participants with multiple fracture regions, the date of the definitive fracture management surgery will be matched to the fracture region with the SSI.

Table 3: CDC Surgical Site Infection Criteria

Outcome	Description
Superficial Incisional SSI	
Date of event for infection occurs from the date of fracture to 30 days after the definitive fracture management surgery (where day 1 = the procedure date)
 
AND
 
involves only skin and subcutaneous tissue of the incision
 
AND
 
patient has at least one of the following:
 
 a. purulent drainage from the superficial incision. b. organisms identified from an aseptically-obtained specimen from the superficial incision or subcutaneous tissue by a culture or non-culture based microbiologic testing method which is performed for purposes of clinical diagnosis or treatment (e.g., not Active Surveillance Culture/Testing [ASC/AST]). c. superficial incision that is deliberately opened by a surgeon, attending physician or other designee and culture or non-culture based testing is not performed. 
AND

Outcome	Description
	
patient has at least one of the following signs or symptoms: pain or tenderness; localized swelling; erythema; or heat.
 
d. diagnosis of a superficial incisional SSI by the surgeon or attending physician or other designee.
 
The following do not qualify as criteria for meeting the definition of superficial SSI:
 
 • Diagnosis/treatment of cellulitis (redness/warmth/swelling), by itself, does not meet criterion “d” for superficial incisional SSI. Conversely, an incision that is draining or that has organisms identified by culture or non-culture based testing is not considered a cellulitis. • A stitch abscess alone (minimal inflammation and discharge confined to the points of suture penetration). • A localized stab wound or pin site infection- Such an infection might be considered either a skin (SKIN) or soft tissue (ST) infection, depending on its depth, but not an SSI 
Note: A laparoscopic trocar site for an operative procedure is not considered a stab wound.
 
 • An infected burn wound is classified as BURN and is not an SSI.
Deep Incisional SSI	
The date of event for infection occurs from the date of fracture to 90 days after the definitive fracture management surgery (where day 1 = the procedure date)
 
AND
 
involves deep soft tissues of the incision (e.g., fascial and muscle layers)
 
AND
 
patient has at least one of the following:
 
 a. purulent drainage from the deep incision. b. a deep incision that spontaneously dehisces, or is deliberately opened or aspirated by a surgeon, attending physician or other designee, and organism is identified by a culture or non-culture based microbiologic testing method which is performed for purposes of clinical diagnosis or treatment (e.g., not Active Surveillance Culture/Testing [ASC/AST]) or culture or non-culture based microbiologic testing method is not performed 
AND
 
patient has at least one of the following signs or symptoms: fever ($>38^{\circ}\text{C}$); localized pain or tenderness. A culture or non-culture based test that has a negative finding does not meet this criterion.
 
 c. an abscess or other evidence of infection involving the deep incision that is detected on gross anatomical or histopathologic exam, or imaging test
Organ/Space SSI	
Date of event for infection occurs from the date of fracture to 90 days after the definitive fracture management surgery (where day 1 = the procedure date)
 
AND
 
infection involves any part of the body deeper than the fascial/muscle layers, that is opened or manipulated during the operative procedure
 
AND
 
patient has at least one of the following:
 
 a. purulent drainage from a drain that is placed into the organ/space (e.g., closed suction drainage system, open drain, T-tube drain, CT guided drainage) b. organisms are identified from an aseptically-obtained fluid or tissue in the organ/space by a culture or non-culture based microbiologic testing method which is performed for purposes of clinical diagnosis or treatment (e.g., not Active Surveillance Culture/Testing [ASC/AST]). c. an abscess or other evidence of infection involving the organ/space that is detected on gross anatomical or histopathologic exam, or imaging test evidence suggestive of infection. 
AND
 
meets at least one criterion for a specific organ/space infection site listed in Table 3 of the CDC Procedure-associated Module (summarized in Table 4 below).²⁵ These criteria are found in the Surveillance Definitions for Specific Types of Infections chapter.³⁷

*The CDC criteria has been modified to include all definitive fracture management surgeries, as opposed to including only National Healthcare Safety Network procedures that require infection reporting.

The CDC criteria for classifying SSIs will be followed. If multiple tissue levels are involved in the infection, the type of SSI (superficial incisional, deep incisional, or organ/space) reported will reflect the deepest tissue layer involved in the infection during the surveillance period. The date of event will be the date that the participant met criteria for the deepest level of infection using the following procedures: 1) report infection that involves the organ/space as an organ/space SSI, whether or not it also involves the superficial or deep incision sites and 2) report infection that involves the superficial and deep incisional sites as a deep incisional SSI. The most relevant National Healthcare Safety Network Organ/Space SSI classifications are summarized in **Table 4**. Whenever possible, the treating surgeon or study personnel should take photos of the infected region to facilitate the adjudication process.

Table 4: Relevant Organ/Space SSI Sites

Organ/Space SSI	BONE	Osteomyelitis
	JNT	Joint or bursa infection
	PJI	Prosthetic joint infection

All reported SSIs will be reviewed independently by an infection preventionist nurse and an orthopaedic surgeon who are members of the Adjudication Committee. Briefly, they will complete the review by examining all relevant information to determine if the SSI meets the CDC criteria of a superficial incisional SSI, deep incisional SSI, or organ/space SSI. The Committee will reach consensus on all reviewed SSIs. A hospital epidemiologist and infectious disease physician who are members of the Adjudication Committee will be available to provide guidance as needed. All members of the Adjudication Committee will be blinded to the treatment allocation.

4.8.2 Secondary Outcome

The secondary outcome is unplanned fracture-related reoperation within 12 months of the fracture(s). This outcome has been used in previous fracture trials and is defined as any unplanned surgery that occurred from the time of injury to 12 months post-injury that is associated with an infection at the operative site or contiguous to it, a wound-healing problem, or a fracture delayed union or nonunion. Common examples include any unplanned: 1) irrigation and debridement of surgical incisions or open fracture wounds due to infections or wound healing problems; 2) revision wound closure for dehiscence; 3) soft tissue coverage procedure for infected or necrotic wound; 4) fracture delayed union or nonunion surgery (such as bone grafting or implant exchange); and 5) reoperation for hardware or prosthesis failure due to infection or bone-healing problems. Removal of hardware for soft tissue prominence or periprosthetic fracture are common examples of reoperations that will not be considered outcome events. To facilitate adjudication, the treating surgeon or study personnel should take photographs of any infections or wound infections. Two orthopaedic surgeons who are members of the Adjudication Committee will independently review all reported unplanned fracture-related reoperations to determine if they meet the criteria for being a study event. The Committee will reach consensus on all reviewed unplanned fracture-related reoperations.

4.8.3 Exploratory Outcomes

Two exploratory definitions of infection will be used for sensitivity analyses of the primary comparison. The first exploratory outcome is fracture-related infection (FRI) within 12 months of the fracture, defined by the confirmatory criteria for FRI outlined in a 2018 consensus definition.³⁸ The FRI criteria has been selected as an exploratory outcome because the CDC criteria has been

criticized for failing to adequately account for the complexities of infections in traumatic fractures.^{38,39} The FRI criteria attempts to improve upon the ability to detect infections specifically in fracture patients; however, this definition of FRI has not been fully validated or widely adopted.

The confirmatory criteria include the presence of one or more of the following signs/symptoms:

- 1) Fistula, sinus or wound breakdown (with communication to the bone or the implant).
- 2) Purulent drainage from the wound or presence of pus during surgery.
- 3) Phenotypically indistinguishable pathogens identified by culture from at least two separate deep tissue/implant (including sonication-fluid) specimens taken during an operative intervention. In case of tissue, multiple specimens (3) should be taken, each with clean instruments (not superficial or sinus tract swabs). In cases of joint effusion, arising in a joint adjacent to a fractured bone, fluid samples obtained by sterile puncture may be included as a single sample.
- 4) Presence of microorganisms in deep tissue taken during an operative intervention, as confirmed by histopathological examination using specific staining techniques for bacteria or fungi.

The second exploratory outcome is SSI using the CDC criteria *within 12 months of the fracture*. This secondary outcome will use the same diagnostic CDC reporting criteria for the primary outcome (**Tables 3 and 4**); however, the timeframe for this outcome will be expanded to include all SSIs that occur within 12 months of fracture. Similar to the rationale for using the FRI outcome, and the recommendations for a minimum of 12 months follow-up for orthopaedic fracture outcomes⁴⁰, this expanded timeframe will detect infections that occur beyond the standard CDC surveillance reporting periods. This modification of the CDC reporting periods has been used in previous orthopaedic fracture trials.^{4,41}

An infection preventionist nurse and an orthopaedic surgeon member of the Adjudication Committee will review all reported SSIs to determine if they meet the FRI confirmatory criteria and / or the CDC criteria following the processes described above (see Section 4.8.1).

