1.6 Why Iodophor Skin Preparations May Reduce Extremity Fracture Reoperations

While the primary rationale for using antiseptic skin preparation solutions is to reduce the risk of SSI, many fracture healing complications are associated with indolent infections. These low-grade infections typically do not exhibit clinical signs consistent with SSI. Instead, they present several months post-fracture fixation and are only detected from deep tissue samples collected during secondary surgeries to treat fractures that fail to heal (nonunion). Previous fracture nonunion

studies have identified an infectious etiology in 31–38% of cases.^{28,29} Similarly, results from the FLOW trial suggest that 58% of the reoperation events were caused by fracture nonunion or a hardware failure related to an infection, wound-healing problem, or bone-healing problem (n= 188/323). This is consistent with the data presented in **Figure 1**, confirming a high proportion of fracture infections requiring surgery occurred beyond the 90-day surveillance period for SSI.¹⁸ Therefore, given the rationale that iodophors may be more effective in preventing SSI, it is clinically plausible that its use may also reduce unplanned fracture-related reoperations.

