### 203 **5.3 Subgroup Analyses**

204 To determine treatment effect heterogeneity on the study outcomes, we will use the same analytical  
205 approach as specified for the primary and secondary outcomes above but include a treatment by  
206 subgroup interaction term in the model. We will report results by the prespecified subgroups,  
207 which consists of the presence or absence of a severe soft tissue injury (defined as severe soft  
208 tissue injury versus no severe soft tissue injury) and the presence or absence of a periarticular  
209 fracture (defined as AO/OTA fracture types 33, 41, 43 and 44 versus all other included fractures).  
210 The results of the subgroup analyses will be reported using a forest plot reporting odds ratios with  
211 95% confidence intervals. These analyses will be approached and reported in accordance with best  
212 practices and guidelines for subgroup analyses. We will use the criteria suggested by  
213 Schandelmaier et al. to guide inferences about the credibility of our subgroup analyses. As  
214 participants may have more than one included fracture representing different subgroups, the

215 analyses will be performed by categorizing participants according to the fracture with the most  
216 severe injury characteristic for each subgroup.

217

218 **5.4 Sensitivity Analyses**

219 We will consider four alternative analysis approaches to evaluate the robustness of our findings,  
220 including alternative definitions of the primary outcome, an as-treated analysis of the primary and  
221 secondary outcomes, a complete case missing data analysis of the primary and secondary  
222 outcomes, and a Bayesian analysis of the primary and secondary outcomes. We will also allow  
223 for post-hoc sensitivity analysis based on information not anticipated in advance.

224

225 *Alternative Definitions of SSI:* To evaluate the robustness of the result, we will consider two  
226 alternative exploratory definitions of SSI: 1) using the confirmatory criteria from the consensus  
227 definition of Fracture-Related Infection (FRI), and 2) expanding the CDC criteria for all types of  
228 SSI to within 1 year of injury.

229

230 Our adjudication of Fracture-Related Infection is defined by the confirmatory criteria outlined in  
231 its 2018 consensus definition. The FRI criteria have been selected as an exploratory outcome  

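### FRI and 12-month CDC infection are adjudicated only when the site reports an SSI; reoperations are not stated to be screened, so late infections found at reoperation may be under-ascertained

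*Protocol*

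**What the plan says.** Protocol 4.8.3 defines two exploratory infection outcomes: FRI by the confirmatory criteria, and SSI by the CDC criteria, both within 12 months of fracture. For both, an infection preventionist nurse and an orthopaedic surgeon "will review all reported SSIs to determine if they meet the FRI confirmatory criteria", the CDC criteria, or both. No other input to this review is given.

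Reoperations follow a different path. Under Protocol 4.8.2, two orthopaedic surgeons "independently review all reported unplanned fracture-related reoperations to determine if they meet the criteria for being a study event". Surgery for delayed union or nonunion, and reoperation for hardware failure due to infection or bone-healing problems, are listed there as examples of the secondary outcome.

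On the course of late infection, Protocol 1.6 says: "These low-grade infections typically do not exhibit clinical signs consistent with SSI". It adds that they appear months after fixation and are detected only in deep tissue sampled at a secondary operation for nonunion.

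Section 5.4 of each SAP introduces FRI with the words "Our adjudication of Fracture-Related Infection is defined by the confirmatory criteria outlined in" the 2018 consensus definition, and then lists the criteria. Neither SAP adds a case-finding route.

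**The concern.** FRI criteria 3 and 4 (matching cultures from at least two deep specimens, or microorganisms on histopathology) require specimens taken during an operation. For a low-grade infection without SSI signs, the operation most likely to supply them is the nonunion or hardware-failure reoperation. Under the written rule, that operation reaches FRI review only if the site also files an SSI report.

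Protocol 4.5 states that the orthopaedic team, including study coordinators, is not blinded. Central blinded adjudication can correct the classification of what it receives. It cannot recover a case that was never sent.

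At stake is the value of a planned robustness check. Protocol 5.2.4, item 7, uses the two definitions to see whether the conclusions are sensitive to how SSI is defined. If the candidates are limited to events already recognised as SSIs, the check may lean toward agreement with the primary result, and 12-month incidence may be understated.

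**Working it through.** **1. Tracing the case-finding route**

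| Step | Source | Reported SSI | Reoperation not reported as SSI |
|---|---|---|---|
| Data collected to 12 months | Protocol Table 2 | Yes | Yes |
| Details named for collection | Protocol 4.8.4 | Include culture results | Date, type and reason as examples; list left open |
| Reviewers | Protocol 4.8.1–4.8.3 | Nurse and surgeon | Two surgeons |
| Question put to reviewers | Protocol 4.8.1–4.8.3 | CDC criteria, FRI criteria | Is it a reoperation event? |
| Review against FRI or 12-month CDC criteria stated | Protocol 4.8.3; SAPs 5.4 | Yes | No |

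The gap is the last cell of the right-hand column.

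**2. The plan's own figures, reproduced**

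- Reoperations in the earlier open-fracture irrigation trial: 323/2,447 = 13.2% (Protocol 1.1 states 13.2%).
- Share due to nonunion or to hardware failure related to infection, wound healing or bone healing: 188/323 = 58.2% (Protocol 1.6 states 58%).

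**3. Illustration of size, open fractures only**

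Inputs:
- 1,540 participants (Protocol 5.1).
- 13.2% reoperation incidence, assumed to carry over from the earlier trial.
- 31–38% of nonunions with an infectious cause (Protocol 1.6).
- 25–58% of reoperations for nonunion or hardware failure. The documents do not give nonunion alone. The 58% is their combined figure and so an upper bound; the 25% is an assumption.

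Infections depending on site SSI reporting = participants × reoperation incidence × share × infectious fraction.

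- Reoperations: 1,540 × 0.132 = 203.
- Nonunion or hardware failure: 203 × 0.25 = 51; 203 × 0.58 = 118.
- Lowest: 51 × 0.31 = 16.
- Highest: 118 × 0.38 = 45.

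For scale, primary SSIs at the planning rates in Protocol 5.1 (12.5% with CHG, risk ratio 0.65, so 12.5% × 0.65 = 8.125% with iodine):

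- 770 × 0.125 + 770 × 0.08125 = 96.3 + 62.6 = 159.
- With 10% loss to follow-up: 159 × 0.9 = 143.

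Before loss to follow-up, 16 to 45 against 159 is 10% to 28% of the expected primary count. Applying the same loss to both leaves that ratio unchanged.

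The documents give no nonunion or reoperation rate for closed fractures, so that population (6,280 participants) is not sized.

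**The case against.** A reader might infer that infections found at nonunion surgery are never assessed for FRI. The documents do not support that. SSI data are collected at every visit to 12 months, with medical record review and retrieval of outside records (Protocol 4.8.4). A reported SSI need not show classic signs: CDC organ/space criterion b accepts organisms from aseptically obtained tissue, and osteomyelitis is a listed site (Protocol Tables 3 and 4). A site can therefore report a culture-positive nonunion as an SSI, and it would then be reviewed. This stands. The exposure is to sites that enter the surgery only as a reoperation.

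Nor do the documents say that the alternative definitions were introduced for indolent infection at nonunion surgery. Section 1.6 makes that argument for the secondary outcome, concluding that "it is clinically plausible that its use may also reduce unplanned fracture-related reoperations". Section 4.8.3 justifies FRI by criticism of the CDC criteria in fractures, and the 12-month window by infections after the CDC surveillance periods. That window still covers late infections, whatever operation reveals them.

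It would also be wrong to say that the alternative definitions cannot diverge from the primary outcome. The longer window adds reported late SSIs, and the FRI criteria can classify the same case differently.

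Three further points carry weight. The reoperation outcome counts nonunion surgery whether or not infection is recognised, and Table 3 of each SAP reports it by type. If under-reporting is similar in both arms, incidence and risk difference shrink, but the odds ratio changes little for uncommon events; no mechanism for a difference between arms is documented beyond unblinded reporting. The case report forms are not in the documents, and the listed reoperation fields are only examples, so cultures may already be captured.

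None of this supplies a stated route from a reoperation to FRI review.

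**Conclusion.** The concern holds as a case-finding gap in two exploratory outcomes. FRI and 12-month CDC adjudication depend on the site reporting an SSI, and reoperations are not stated to be screened against either definition. The outcomes may be under-ascertained, and the sensitivity check may lean toward agreement with the primary result. The primary and secondary analyses are unaffected, and both SAPs treat sensitivity results as exploratory (section 3.1).

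The 16 to 45 open-fracture infections are those that would depend on site SSI reporting, not infections missed. The range assumes that the earlier trial's reoperation rate carries over, that 25–58% of reoperations are of the relevant kind, and that the infectious fraction quoted for nonunions applies to all of them. Some are infection or wound reoperations that sites would probably report as SSIs anyway. The number actually lost could be small and cannot be derived from the documents. The change is still worth making because the rule as written leaves a prespecified robustness check to unblinded site reporting, and correcting it costs little.

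**What to change.** In Protocol 4.8.3, extend the input to the FRI and 12-month CDC review so that it covers every reported unplanned fracture-related reoperation as well as every reported SSI. State the same rule in section 5.4 of both SAPs.

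For each reoperation, have the existing Adjudication Committee record whether the FRI confirmatory criteria and the 12-month CDC criteria are met, from the operative note and any culture or histology results already obtained. Events that may meet either set of criteria should pass to the existing nurse–surgeon pair, so that the CDC criteria are not applied by surgeons alone and the nurse need not review every reoperation.

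The cost is modest added adjudication time and retrieval of existing culture and histology results. It needs no new assessor and no patient procedure.

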4.8.4 Data Collection and Participant Follow-up

After obtaining informed consent, study personnel will record the baseline data on the study CRFs. They will obtain this information directly from the participant or proxy, from the participant's medical chart, and the participant's treating orthopaedic surgeon or other health care providers. Data collection points include participant characteristics and injury details such as age, gender, comorbidities, mechanism of injury, and other injuries. Study personnel will also record the characteristics of up to three eligible fracture regions including the bone(s) fractured, fracture severity, size of the wound (if applicable), and degree of soft tissue injury using the Tscherne classification in closed fractures and the Gustilo classification in open fractures.^{1,34,36}

Surgical data and in-hospital data will be collected throughout the participant's hospital stay. Detailed information will be collected regarding the surgical management of their fracture(s), including the timing of the surgery(ies) and the method of initial and definitive fracture treatment. For open fracture regions, study personnel will also record the use of staged debridements, the presence or lack of skin closure between debridements, and the use of local antibiotics at the wound. Lastly, study personnel will record the use of negative pressure wound therapy for open wounds or in the presence of open wounds surgically closed. These treatment decisions are

hypothesized to be associated markers of injury severity and potential confounders of the study interventions.

Study participants will be followed at 6 weeks, 3 months, 6 months, 9 months, and 12 months from their fracture. SSIs and unplanned fracture-related reoperations will be identified at the time of diagnosis/occurrence and/or during each participant's clinical assessment and medical record review that will occur during their routine outpatient clinic visits (**Table 2**). Detailed information on the SSI including the date of diagnosis, participant signs and symptoms, culture test results, method of treatment(s), and date of resolution will be collected. Study personnel will also record details about the participants' reoperations on the CRFs (e.g., date of reoperation, type of procedure, reason for procedure, etc.). In cases where the participant does not return to the clinic, study personnel will contact the participant by telephone, text, email, and standard mail and will review their medical record for any SSIs or fracture-related reoperations. If the participant reports being treated at another hospital, study personnel will obtain the medical records from the other hospital. We have used this approach in our other multi-center trials (e.g., SPRINT, TRUST, FLOW, FAITH, HEALTH, etc.).^{4,41-44}

To ensure research participant safety, serious adverse events (SAEs) will be documented at each follow-up visit and promptly submitted to the Methods Center and the local or central Institutional Review Board (IRB) or Research Ethics Board (REB) as per the required reporting processes.

Several strategies may be used to maximize follow-up including: 1) at the time of enrollment, each participant will provide their own telephone number, as well as the name and address of a primary care physician, and the names and phone numbers of three people at different addresses with whom the participant does not live with and who are likely to be aware of the participant's whereabouts; 2) participants will receive a reminder card upon discharge for their next follow up visit by the clinical site study personnel; 3) participants will receive text message reminders; 4) follow-up will coincide with normal surgical fracture clinic visits; and 5) if a participant refuses or is unable to return for the follow-up assessment, study personnel will determine his/her status with regard to major study outcomes by telephone, text, mail, or email contact with the participant or the provided alternate contacts. Given these are standard of care visits and the participants will be receiving ongoing orthopaedic care for their acute fractures, minimal loss to follow-up is expected. Using these techniques, we expect greater than 95% follow-up at 3 months and 90% follow-up at 12 months post-fracture.

Participants will not be deemed lost to follow-up until the 12-month visit is overdue and all attempts to contact the participant have been exhausted. Participants will not be withdrawn from the study if the study protocol was not adhered to (e.g., allocated treatment not received, missed follow-up visits, etc.). The reasons for participants being withdrawn from the study will be documented (e.g., withdrawal of consent or lost to follow up).

